3.3.1 Other Considerations

The participating healthcare professionals must be familiar with the use of both Theranova 400 dialyzer and Elisio-17H dialyzer. All participating healthcare professionals will be trained on both types of dialyzers before the first patient is treated.

3.4 Study Duration and Dates

Patients will undergo 3 dialysis sessions per week, for 24 weeks. The participating patients should continue with their pre-study HD prescriptions (in terms of treatment time, blood flow rate and dialysate flow rate) and prescriptions should be kept stable throughout the study.

3.5 Study Discontinuation Rules

The study should be suspended if suspicion of an unacceptable risk to the patients arises during the clinical investigation, or when instructed by the Institutional Review Board

(IRB) or regulatory authorities. Risks to patients could be indicated when any of the following events occur:

- Device malfunction, considered by the investigators and/or Baxter Healthcare as possibly leading to a deficiency in the patient's treatment
- Repeated patient discomfort with the product
- Unexpected/Unanticipated Serious Adverse Device Effect (SADE)

The Sponsor shall review untoward events and assess risks during the conduct of the clinical investigation. Decision to restart the study will be made jointly by Baxter Healthcare and the coordinating investigator following evaluation of the problems encountered and implementation of mitigation steps. The Sponsor shall terminate the clinical investigation if an unacceptable risk is confirmed to be not mitigatable.

3.5.1 Procedure for Resuming the Clinical Investigation after Temporary Suspension

When the Sponsor concludes an analysis of the reasons(s) for the study suspension, implements the necessary corrective actions and decides to lift the temporary suspension, the Sponsor shall inform the principal investigators (PIs), the IRB, and where appropriate, the regulatory authority of the rationale and provide them with the relevant data supporting this decision.

Concurrence shall be obtained from the IRB and, where appropriate, regulatory authorities before the clinical investigation resumes.

If patients have been informed of the suspension, the PI or authorized designee shall inform them of the reasons for resumption.

4. STUDY POPULATION SELECTION

4.1 Study Population

The study population consists of subjects with ESRD who have been stable and receiving HD therapy at least 3 times a week for 3 months prior to enrollment. A sufficient number of patients will be enrolled in the study in order to randomize 166 patients in a 1:1 manner to either Theranova 400 dialyzer or the Elisio-17H dialyzer. The study will be conducted in up to 30 study centers in the USA.

4.2 Inclusion Criteria

All of the following criteria must be met for the patient to be enrolled in this study.

1. ESRD patients age 22 and older, or between ages 18 and 21 with a weight ≥ 40 kg.
2. Clinically stable as judged by the treating physician and as demonstrated by stable medical history for 30 days prior to enrollment, physical examination, and laboratory testing.
3. Hemodialysis therapy with high-flux dialyzers for at least 3 months immediately prior to study enrollment and expected to survive for the next 12 months.
4. Expected to maintain an acceptable urea clearance (Kt/V) with a dialyzer of an approximate surface area of 1.7 m^2 .
5. Currently being dialyzed at an in-center setting, on a schedule of 3 times per week.
6. Able to give informed consent after an explanation of the proposed study, and who are willing to comply with the study requirements for therapy during the entire study treatment period.
7. Have a stable functioning vascular access (arteriovenous fistula, graft, or dual-lumen tunneled catheter); stable access will be confirmed by observed Kt/V ≥ 1.2 for past 2 measurements and/or achievement of within 15% the prescribed blood flow rate over 3 treatments prior to study entry.

4.3 Exclusion Criteria

Patients who meet any of the following criteria will be excluded from the study. This study will exclude subjects who:

1. Are female and pregnant, lactating, or planning to become pregnant during the study period. Note: Female subjects of childbearing potential, defined as women < 55 years old who has not had a partial or full hysterectomy or oophorectomy, must have a negative serum beta human chorionic gonadotropin (β -hCG) pregnancy test at screening. Subjects of childbearing potential must use a medically acceptable means of contraception during their participation in the study.
2. Have chronic liver disease.
3. Have a known paraprotein-associated disease.
4. Have known bleeding disorders (e.g., gastrointestinal bleed, colonic polyps, small bowel angiodyplasia, and active peptic ulcers).

5. Have had a major bleeding episode (i.e. soft tissue bleeding, blood in stool, prolonged nose bleeds, joint damage, retinal bleeding, extensive mucosal bleeding, exsanguination, cerebral hemorrhage) \leq 12 weeks prior to randomization.
6. Have had a blood (red blood cell) transfusion \leq 12 weeks prior to randomization.
7. Have had an acute infection \leq 4 weeks prior to randomization.
8. Have active cancer, except for basal cell or squamous cell skin cancer.
9. Have a known serum κ/λ FLC ratio that is less than 0.37, or greater than 3.1.^b
10. Have a known monoclonal gammopathy (monoclonal gammopathy of uncertain significance, smoldering [asymptomatic] multiple myeloma, symptomatic multiple myeloma, plasmacytomas, or plasma cell leukemia).
11. Have a known polyclonal gammopathy (connective tissue disease, liver disease, chronic infection, lymphoproliferative disorder, or other hematologic conditions).
12. Have a positive serology test for human immunodeficiency virus or hepatitis infection.
13. Have a significant psychiatric disorder or mental disability.
14. Are scheduled for planned interventions requiring hospitalization $>$ 1 week.
15. Are scheduled for living-donor transplantation within the study period + 3 months, plan to change to PD therapy within the next 9 months, plan to change to a home hemodialysis treatment, or plan to relocate to an area where no study center is located.
16. Are currently participating in another interventional clinical study or has participated in another interventional clinical study in the past 3 months.
17. Have a history of non-compliance with HD as assessed by an investigator.
18. Have had a major cardiovascular or cerebrovascular event within 3 months of study entry.
19. Have a history with consistent evidence of intradialytic hypotension.
20. Have uncontrolled (systolic blood pressure (BP) $>$ 180 mmHg) hypertension.
21. Have had adverse reactions to dialyzer materials.

^b In patients with renal impairment 0.37 to 3.1 is the normal range for serum κ/λ FLC ratio.

[REDACTED]

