8.4.1 Assessments and Procedures

After providing written informed consent, patients will enter the Screening period. The aim of the Screening period is to assess the eligibility of patients for randomization and participation in the study. The maximum duration of the Screening period is 2 weeks. Screening period of 2 weeks was designed to provide adequate time to obtain screening lab results and complete all screening procedures. This period may not be used to repeat tests if initial tests result in study exclusion.

A complete medical history will include a review for all major body systems and renal history (primary etiology of renal disease, and current HD prescription). Medical history will also include an assessment of all medications being taken at the time of Screening, and any ESA taken in the 30 days prior to Screening, with each medication having a corresponding indication recorded on the concomitant medication eCRF form. Treatment parameters as described in Section 8.5.1 will be collected during treatment visits.

Further assessments include:

- Demographics
- Physical examination
- Vital signs
- Pregnancy test for women with child bearing potential
- AEs/SAEs

- Clinical laboratory evaluation as outlined in [Appendix 2](#)
- Randomization

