Appendix 2 Schedule of Clinical Laboratory Evaluations

Evaluation	Screening Visit Days -14 to -1		Treatment Period												End of Study Visit	
			Visit 1 1 st Treatment Day		Visit 2 Week 4		Visit 3 Week 8		Visit 4 Week 12		Visit 5 Week 16		Visit 6 Week 20		Visit 7 Week 24	
	Pre-dialysis	Post-dialysis	Pre-dialysis	Post-dialysis	Pre-dialysis	Post-dialysis	Pre-dialysis	Post-dialysis	Pre-dialysis	Post-dialysis	Pre-dialysis	Post-dialysis	Pre-dialysis	Post-dialysis	Pre-dialysis	Post-dialysis
β-hCG ^a	X															
λ FLC ^b	X		X		X	X									X	X
β2 Microglobulin			X		X	X									X	X
Serum Albumin	X		X		X		X		X		X		X			X
Liver function ^c	X								X							X
CFD ^d			X		X	X									X	X
IL-6			X		X	X									X	X
TNFα			X		X	X									X	X
κ FLC ^b	X		X		X	X									X	X
Vitamin A			X		X										X	
BUN	X	X			X	X	X	X	X	X	X	X	X	X		
Factor VII			X						X						X	
Protein C			X						X						X	
Factor II			X						X						X	
hs-C-Reactive Protein	X		X		X		X		X		X		X			
Hematology ^e	X		X						X							X
HAV ^f , HBV ^g , HCV ^h , HIV ⁱ	X															

Coagulation ^j	X							X										X	
Serum phosphorus	X		X					X										X	
Comprehensive metabolic panel ^k	X		X					X										X	
Lipids ^l	X		X					X										X	

Notes: All sampling visits will be performed during the mid-week treatment

A serum beta human chorionic gonadotrophin (β -hCG) will be performed within 3 weeks prior to the 1st treatment in the study for women of childbearing potential

^a Female subjects of childbearing potential, defined as a woman <55 years old who has not had a partial or full hysterectomy or oophorectomy, must have a negative serum β -hCG pregnancy test at Screening. Subjects of childbearing potential must use a medically acceptable means of contraception during their participation in the study

^b Lambda free light chains and Kappa free light chains

^c Include: Alkaline phosphatase (ALK-P), Alanine aminotransferase (ALT; SGPT), Aspartate aminotransferase (AST; SGOT), and Gamma-glutamyl-transferase (GGT), total bilirubin, direct bilirubin, globulin, total protein

^d Complement Factor D

^e Includes: Hemocrit, Hemoglobin, Mean corpuscular hemoglobin (MCH), Mean corpuscular hemoglobin concentration (MCHC), Mean corpuscular volume (MCV), Platelet count, Red blood cell (RBC) Count, White blood cell (WBC) Count with Differential

^f Hepatitis A Virus

^g Hepatitis B Virus

^h Hepatitis C Virus

ⁱ Human Immunodeficiency Virus

^j Includes: PT (INR), PT (Sec), aPTT

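### Exclusion 1 defines childbearing potential so that a woman under 55 with a partial or one-sided oophorectomy can enter with no required pregnancy test or contraception

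*Protocol*

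**What the plan says.** Protocol 4.3, criterion 1, has three parts.

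- A general exclusion, which applies to every female subject: those who "Are female and pregnant, lactating, or planning to become pregnant during the study period".
- A testing rule: female subjects of childbearing potential "must have a negative serum beta human chorionic gonadotropin" result at screening.
- A contraception rule: "Subjects of childbearing potential must use a medically acceptable means of contraception during their participation in the study".

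The second and third parts depend on one definition. Childbearing potential is "defined as women < 55 years old who has not had a partial or full hysterectomy or oophorectomy". Footnote a to the laboratory schedule in Protocol Appendix 2 and footnote a to SAP Table 2 (SAP 5.5.1) carry the same definition, again a woman under 55 "who has not had a partial or full hysterectomy or oophorectomy". The screening procedures in Protocol 8.4.1 list the test as "Pregnancy test for women with child bearing potential". Protocol Table 1 and SAP Table 7 list β-hCG as done where applicable, and both laboratory schedules mark it at screening only.

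**The concern.** The definition decides who is tested and who must use contraception. Its surgical exemption makes sense where the operation has removed the ability to conceive. The oophorectomy part goes further, because nothing in the text limits it to removal of both ovaries. A woman with a uterus and some ovarian tissue may still conceive, or may already be pregnant without knowing it, yet the wording places her with women who cannot.

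The sponsor chose to exclude pregnancy and to verify this by a blood test rather than by history alone. For the women concerned, that verification is missing. The device is investigational, and Protocol 1.2 acknowledges that it removes more albumin per treatment than high-flux dialyzers. An undetected pregnancy would be exposed to it in a trial that meant to prevent this.

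**Working it through.** No arithmetic bears on the definition, so the check is a reading of the text in three steps.

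**1. Scope of the phrase *partial or full*.** It can be read in two ways.

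| Reading | Partial oophorectomy | One ovary removed | Result for a woman under 55 who keeps her uterus and some ovarian tissue |
|---|---|---|---|
| A: it modifies both operations | Exempt in terms | Exempt, since she has had an oophorectomy, whether it is called partial or full | Outside the definition |
| B: it modifies hysterectomy only | Exempt if the operation counts as an oophorectomy | Exempt, since the unqualified word covers removal of one ovary | Outside the definition |

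The gap is present under both readings. It closes only if a site reads in a limit to removal of both ovaries, which neither document states.

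**2. Whether another passage closes it.**

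- Protocol 8.4.1 limits the screening test to the same defined group.
- The general note in Protocol Appendix 2 says that β-hCG "will be performed within 3 weeks prior to the 1st treatment in the study for women of childbearing potential", which is again the same group. The notes to SAP Table 2 say the same.
- Both schedules show β-hCG at screening only, so no later visit in the 24 weeks would catch a pregnancy.
- Protocol 4.5 lists pregnancy among the reasons for which a patient may be withdrawn. That operates only once a pregnancy is known.

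No passage requires a test or contraception of a woman outside the definition.

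**3. Whether such a woman could be enrolled.** Protocol 4.2, criterion 1, admits adults from 18 (with a weight condition up to age 21) and sets no upper age limit. Women of reproductive age are therefore eligible, and no other criterion excludes a woman because of a previous oophorectomy.

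The definition is worded alike in all three places. This is a defect in one definition, not a contradiction between passages.

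**The case against.** The strongest reply is that the general exclusion does not depend on the definition. Every woman who is known to be pregnant, or who plans a pregnancy, is excluded. A medical history that includes surgical procedures is taken at screening (Protocol 6.2), so an investigator would see the operation and could order a test. The definition is otherwise broad: under 55 it exempts nobody for menopause or tubal ligation. A site might also take the bare word oophorectomy to mean removal of both ovaries. Finally, the documents describe no fetal risk specific to the device.

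Most of this stands, and it limits the point. Such women *can* enter untested; the documents do not show that they will. The general exclusion and the history help only where pregnancy is known, suspected or planned. The test exists for the remaining cases, and the text leaves it to each site's interpretation.

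A reader might infer two further problems that the documents do not support.

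- *Conflicting test windows.* The three-week note in Appendix 2 may seem to clash with testing at screening, given that "The maximum duration of the Screening period is 2 weeks". It does not. Screening runs from Day -14 to Day -1, so a screening test is taken at most 14 days before Day 1 (15 if a Day 0 is counted), and both are below 3 × 7 = 21 days. A test done at screening meets both statements, and the narrower one governs.
- *Lost week 24 primary endpoints.* Protocol 4.5 says that patients may be withdrawn for pregnancy, not that they must be, and asks that the follow-up procedures be attempted. Missing primary data are handled by multiple imputation (Protocol 10.5, SAP 7.2.2). Loss of endpoint data does not follow from the definition.

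**Conclusion.** The point holds as a drafting defect in a participant safeguard. Under either reading of the phrase, the literal rule releases a woman under 55 with a partial or one-sided oophorectomy from both the pregnancy test and the contraception requirement. For her, neither is required at any time in the study. This works against the purpose of the criterion in which the definition stands.

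The size is limited. The documents give no count of women with this history, and the number is probably very small. Known or planned pregnancy still excludes them. Sample size, power, type I error and the endpoint analyses are unchanged.

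The conclusion rests on two assumptions. One is general medical knowledge, not stated in the documents: a woman with a uterus and remaining ovarian tissue may be able to conceive. The other is that sites apply the definition as written. The consent form was not available, so any pregnancy wording in it could not be checked.

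**What to change.** Correct the definition so that the oophorectomy exemption covers only women with no remaining ovarian tissue, for example by specifying bilateral oophorectomy. The hysterectomy part can stay. Make the same change in Protocol 4.3 criterion 1, Protocol Appendix 2 footnote a and SAP Table 2 footnote a. The SAP footnote does not govern eligibility, but it should match the protocol. The change brings the definition into line with the criterion's own purpose of excluding pregnancy.

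The cost is a protocol amendment, which needs IRB approval before it is implemented (Protocol 11.2) at up to 30 centers, and a matching edit to the SAP. A few more women would have a β-hCG test, on blood already drawn at screening, and would come under the existing contraception requirement. No analysis changes.

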4.4 Recruitment

Recruitment for the study will commence after review and approval from the IRB for each respective study center. After the patient has received the Informed Consent Form (ICF) and allowed time to consider their participation in the study, inclusion and exclusion criteria will be verified. Patients will be considered enrolled in the study once the ICF has been signed and inclusion/exclusion criteria have been confirmed.

4.5 Removal of Patients from Therapy, Assessment, or Study

Patients are considered withdrawn/prematurely discontinued from the study if their participation is discontinued before completion of the required evaluations as described in this protocol. Patients may be withdrawn/prematurely discontinued for any of the following reasons:

1. AE
2. Inadequate dialysis based on Investigator judgement
3. Protocol violations (i.e. the patient fails to meet protocol entry criteria or does not adhere to protocol requirements)
4. Pregnancy
5. Lost to follow-up (i.e. patient fails to return for study visits)
6. Voluntary withdrawal (i.e. patient's request)
7. Termination of study
8. Investigator's discretion
9. Renal transplantation
10. Switch to PD
11. Death
12. Change to another dialysis center, that is not a clinical study site
13. Missing 3 consecutive study treatments
14. Other reason (with reason noted on the electronic case report form [eCRF])

The Investigator may terminate a patient's study participation at any time during the study if he/she judges it to be in the patient's best interest. In addition, a patient may discontinue his or her participation any time during the study without having to justify his/her decision. If a patient's participation is discontinued, the reason(s) must be recorded in the source documents and on the eCRF. If a patient discontinues for any reason, every effort should be made to perform all of the procedures that are scheduled

for the follow-up visit occurring at the pre-dialysis on the next treatment day. In addition, SAEs (related or not) and adverse device effects (ADEs), will be followed until resolution or stable, including following the patient after the end of the study if necessary. The Investigator or designee should inform their site monitor the moment any patient is withdrawn or discontinued from the study, regardless of the reason(s) for withdrawal or discontinuation.

4.6 Missed Visits

In general, missed dialysis session visits will not be replaced. If a patient misses a mid-week dialysis session, where a study treatment visit was scheduled to occur, the missed study visit procedures will be performed during the next mid-week dialysis session and subsequent visits and follow-up visit will occur as planned. However, if the patient fails to return for that mid-week dialysis session and also misses the subsequent week (a third mid-week session), then the patient will be terminated from the study. Study termination also applies if the patient misses 3 consecutive study treatments (i.e. missing a full week of dialysis). Reasons for missed visits will be captured on the eCRF.

5. STUDY TREATMENT(S)

5.1 Description of Treatment(s)

5.1.1 Study Device – Theranova 400 dialyzer

Theranova dialyzers are indicated for treatment of chronic and acute renal failure by dialysis. This study is intended to support an indication for extended hemodialysis to remove middle molecular uremic toxins.

The membrane used in Theranova 400 dialyzer is a blend of polyarylethersulfone and polyvinylpyrrolidone. Each hollow fiber has an inner diameter of approximately 180 μm and a wall thickness of approximately 35 μm , the effective membrane length is 236 mm, with an effective surface area of 1.7 m^2 . On each end of the device the hollow fibers are potted in polyurethane (PUR) to isolate the blood compartment from the filtrate dialysate compartment. The housing and the end caps of the dialyzer are made of polycarbonate. Dialysis fluid and blood connectors are designed according to ISO 8637. Theranova 400 dialyzer is sterilized by steam, according to ISO 17665-1.

5.1.2 Study Device – Elisio-17H dialyzer

The membrane used in the Elisio-17H dialyzer (PolynephronTM) is made of Polyethersulfone and Polyvinylpyrrolidone. The fiber walls are 40 μm thick, and have an internal diameter of about 200 μm . The effective length is 271 mm, with an effective surface area of 1.7 m^2 . On each end of the device the hollow fibers are potted in PUR to

isolate the blood compartment from the filtrate dialysate compartment. The housing and the end caps of the dialyzer are made of Polypropylene. The Elisio-17H dialyzer is sterilized by dry gamma irradiation.

Hemodialysis with an Elisio-17H hemodialyzer is indicated for patients with acute or chronic renal failure when conservative therapy is judged to be inadequate. It may also be indicated in the treatment of patients intoxicated with poisons or drugs. It is FDA cleared under 510(k) K131935.

5.2 Treatments Administered

All randomized patients will receive dialysis treatments with either Theranova 400 dialyzer or Elisio-17H dialyzer, 3 times weekly for a period of 24 weeks. Trained HD staff will administer all treatments.

5.3 Selection and Timing for Each Patient

Treatments will occur at sites that routinely implement high-flux dialysis. Dialysis prescription and management will be performed per institutional practice. All patients will receive in-center HD treatments, 3 times per week for a total of 24 weeks using the study device which he/she has been randomized to. Actual treatment duration of the individual dialysis session will vary based on clinical requirements determined by the treating physician.

Hemodialysis treatment duration per session for each individual patient will vary based on clinical requirements determined by the Investigator, based on the patient's need, residual renal function (via estimated Glomerular Filtrations Rate), access function, tolerance to HD and other relevant factors. The participating patients' HD prescriptions should be kept stable throughout the study; any changes to the prescriptions must be recorded.

